## 12. IMPORTANT MEDICAL PROCEDURES TO BE FOLLOWED BY THE INVESTIGATOR

## 12.1 Medical emergencies and AstraZeneca contacts

The Principal Investigator(s) is responsible for ensuring that procedures and expertise are available to handle medical emergencies during the study. A medical emergency usually constitutes a SAE and is to be reported as such. In the case of a medical emergency the investigator may contact the Study Team Physician.

#### 12.2 Overdose

There is currently no specific treatment in the event of overdose with olaparib and possible symptoms of overdose are not established. Olaparib must only be used in accordance with the dosing recommendations in this protocol. Any dose or frequency of dosing that exceeds the dosing regimen specified in this protocol should be reported as an overdose. The Maximum Tolerated Dose is 300 mg bid (tablet).

Adverse reactions associated with overdose should be treated symptomatically and should be managed appropriately.

An overdose with associated AEs is recorded as the AE diagnosis/symptoms on the relevant AE modules in the eCRF and on the Overdose CRF module.

An overdose without associated symptoms is only reported on the Overdose CRF module.

If an overdose on an AstraZeneca study drug occurs in the course of the study, then investigators or other site personnel inform appropriate AstraZeneca representatives within one day, i.e., immediately but no later than the end of the next business day of when he or she becomes aware of it.

The designated AstraZeneca representative works with the investigator to ensure that all relevant information is provided to the AstraZeneca Patient Safety data entry site.

For overdoses associated with SAE, standard reporting timelines apply. For other overdoses, reporting should be done within 30 days.

## 12.3 Pregnancy

All outcomes of pregnancy should be reported to AstraZeneca.

### 12.3.1 Paternal exposure

Male patients should refrain from fathering a child or donating sperm during the study and for 3 months following the last dose.

Pregnancy of the patient's partners is not considered to be an adverse event. However, the outcome of all pregnancies (spontaneous miscarriage, elective termination, ectopic pregnancy, normal birth or congenital abnormality) should, if possible, be followed up and documented.

The outcome of any conception occurring from the date of the first dose until 3 months *after the last dose* should be followed up and documented.

Archival Tissue Sample j	X							
Prostatectomy k						X		

NOTE: [X] denotes an optional procedure for that day.

<sup>a Unscheduled visits can be performed at any time to assess the patient for an adverse event or at the discretion of the Investigator.

- b The safety follow-up visit will be conducted approximately 30 days (± 5 days) after the last dose of Olaparib or prior to the initiation of a new systemic antineoplastic therapy or investigational agent, whichever occurs first.
- Patients will undergo a complete physical examination at the Screening visit and Day 90 visit. For other assessments: limited physical examination (directed towards patient reported symptoms; areas of cancer spread; and cardiac, respiratory, and gastrointestinal systems).
- d Digital rectal examination should be performed either by the urologic surgeon or the investigator, if not previously performed.
- e Patients will undergo bone scan and computerized tomography (CT)/magnetic resonance imaging (MRI) of the pelvis if defined as having high risk disease or at the investigator's discretion. Any evaluable and measurable disease must be documented within 4 weeks prior to enrollment with a CT scan and/or bone scan (bone scans obtained within 8 weeks will be acceptable). Imaging of the chest, abdomen or head should be performed if clinically indicated.
- Height only at baseline. Weight and vital signs (blood pressure, heart rate, and temperature) will be taken at each visit. These assessments do not need to be repeated at the Baseline Visit if screening assessments were completed ≤4 days prior to first dose.
- Blood will be collected and sent to the local laboratory for the analysis of the following: clinical chemistry, hematology, PSA, serum testosterone. Baseline: collect if screening assessments were done > 28 days prior. Additional blood will be collected at Baseline and followup visits for ctDNA and plasma.
- h Research blood drawn per laboratory manual
-  Therapy will continue for 90 days and be discontinued 1 day before prostatectomy for all patients. If prostatectomy is delayed, dispense an additional bottle of olaparib.
- Tissue from the diagnostic biopsy will be requested (tissue blocks wherever possible; if not possible, 10 unstained slides are to be sent to the study site. See the Lab Manual for processing instructions. Pathology report (including the assessment of the local pathologist regarding Gleason score) from diagnostic biopsy must accompany registration materials.
- Radical prostatectomy should occur on Day 90; a window of ±14 days is permitted, however oral dosing should continue until 1 day before surgery. Preoperative and postoperative evaluation and treatment will be administered as per the instructions of the surgeon.
- ECG is required within 28 days prior to starting study treatment and when clinically indicated.

## **Appendix A: Eastern Cooperative Oncology Group Performance Status**

Grade	Eastern Cooperative Oncology Group (ECOG) Performance Status			
0	Fully active, able to carry on all pre-disease performance without restriction			
1	Restricted in physically strenuous activity but ambulatory and able to carry out work of a light or sedentary nature, e.g., light house work, office work			
2	Ambulatory and capable of all self-care but unable to carry out any work activities. Up and about more than 50% of waking hours			
3	Capable of only limited self-care, confined to bed or chair more than 50% of waking hours			
4	Completely disabled. Cannot carry on any self-care. Totally confined to bed or chair			
5	Dead			

## Appendix B Actions Required in Cases of Increases in Liver Biochemistry and Evaluation of Hy's Law

#### Introduction

This Appendix describes the process to be followed in order to identify and appropriately report cases of Hy's Law. It is not intended to be a comprehensive guide to the management of elevated liver biochemistries. Specific guidance on the managing liver abnormalities can be found in Section 5.4.13 of the protocol.

During the course of the study the Investigator will remain vigilant for increases in liver biochemistry. The investigator is responsible for determining whether a patient meets potential Hy's Law (PHL) criteria at any point during the study.

The Investigator participates, in review and assessment of cases meeting PHL criteria to agree whether Hy's Law (HL) criteria are met. HL criteria are met if there is no alternative explanation for the elevations in liver biochemistry other than Drug Induced Liver Injury (DILI) caused by the Investigational Medicinal Product (IMP, olaparib).

The Investigator is responsible for recording data pertaining to PHL/HL cases and for reporting Adverse Events (AE) and Serious Adverse Events (SAE) according to the outcome of the review and assessment in line with standard safety reporting processes.

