Starting on Day 1, all patients will ingest olaparib (300 mg twice daily) at the same times each day, without breaks (except as outlined for toxicity), for 90 days. The 90 day duration is chosen as a duration adequate to assess impact of neoadjuvant therapy on downstaging but not so prolonged that if patients do not respond to therapy, that potentially curative local therapy is being significantly delayed. Multiple studies have demonstrated in unselected populations that 90 day delay to surgery is not associated with any change in long term outcomes . During neoadjuvant therapy, dose reduction of olaparib is allowed for toxicity as detailed in the protocol. Patients should receive olaparib until 1 day prior to prostatectomy, until the

patient can no longer tolerate the treatment due to an adverse event, until the patient initiates another systemic antineoplastic drug or an investigational drug, or at the discretion of the Investigator. Safety and tolerability will be documented throughout the study and 30 days after prostatectomy by assessment of adverse events, vital signs, and laboratory assessments as defined in the Schedule of Activities. All adverse events will be monitored and recorded until the Safety Follow-up visit. Adverse events will be graded according to the National Cancer Institute Common Terminology Criteria for Adverse Events, Version 4.03 (NCI-CTCAE v4.03). In the event a patient discontinues olaparib due to a related adverse event, follow up will continue until adequate resolution of the adverse event, the physician deems the adverse event to be stable, the patient initiates another systemic antineoplastic drug or an investigational drug, or the patient withdraws consent from the study. A safety follow-up visit will be conducted approximately 30 days after the last dose of olaparib or before the initiation of a new systemic antineoplastic therapy or investigational agent, whichever occurs first. Any ongoing adverse event thought to be related to study treatment will be followed until the event has resolved to baseline grade, the event is assessed by the Investigator as stable, the patient initiates another systemic antineoplastic drug or an investigational drug, the patient is lost to follow-up, the patient withdraws consent, or it has been determined that study treatment or participation is not the cause of the adverse event.

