## 5.4.12 Management of non-hematological toxicity

Repeat dose interruptions are allowed as required, for a maximum of 4 weeks on each occasion. If the interruption is any longer than this the study monitor must be informed. Where toxicity reoccurs following re-challenge with study treatment, and where further dose interruptions are considered inadequate for management of toxicity, then the patient should be considered for dose reduction or must permanently discontinue study treatment.

Study treatment can be dose reduced to 250 mg bid as a first step, and to 200 mg bid as a second step. Treatment must be interrupted if any NCI-CTCAE grade 3 or 4 adverse event occurs which the investigator considers to be related to administration of study treatment.

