#### Potential Hy's Law Criteria met

If the patient does meet PHL criteria the Investigator will:

• Notify the AstraZeneca representative

The Study Physician contacts the Investigator, to provide guidance, discuss and agree an approach for the study patients' follow-up and the continuous review of data. Subsequent to this contact the Investigator will:

- Monitor the patient until liver biochemistry parameters and appropriate clinical symptoms and signs return to normal or baseline levels, or as long as medically indicated
- Investigate the etiology of the event and perform diagnostic investigations as discussed with the Study Physician.
- Complete the three Liver CRF Modules as information becomes available
- If at any time (in consultation with the Study Physician) the PHL case meets serious criteria, report it as an SAE using standard reporting procedures

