#### Review and Assessment of Potential Hy's Law Cases

The instructions in this Section should be followed for all cases where PHL criteria are met.

No later than 3 weeks after the biochemistry abnormality was initially detected, the Study Physician contacts the Investigator in order to review available data and agree on whether there is an alternative explanation for meeting PHL criteria other than DILI caused by the IMP. The AstraZeneca Medical Science Director and Global Safety Physician will also be involved in this review together with other subject matter experts as appropriate.

According to the outcome of the review and assessment, the Investigator will follow the instructions below

If there is an agreed alternative explanation for the ALT or AST and TBL elevations, a determination of whether the alternative explanation is an AE will be made and subsequently whether the AE meets the criteria for a SAE:

- If the alternative explanation is **not** an AE, record the alternative explanation on the appropriate CRF
- If the alternative explanation is an AE/SAE, record the AE /SAE in the CRF accordingly and follow the AZ standard processes

If it is agreed that there is **no** explanation that would explain the ALT or AST and TBL elevations other than the IMP:

- Report an SAE (report term 'Hy's Law') according to AstraZeneca standard processes.
  - The 'Medically Important' serious criterion should be used if no other serious criteria apply
  - As there is no alternative explanation for the HL case, a causality assessment of 'related' should be assigned.

If there is an unavoidable delay of over 3 weeks in obtaining the information necessary to assess whether or not the case meets the criteria for HL, then it is assumed that there is no alternative explanation until such time as an informed decision can be made:

- Report an SAE (report term 'Potential Hy's Law') applying serious criteria and causality assessment as per above
- Continue follow-up and review according to agreed plan. Once the necessary supplementary information is obtained, repeat the review and assessment to determine whether HL criteria are met. Update the SAE report according to the outcome of the review

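### Appendix B sends liver management to a section that does not exist, and no rule requires olaparib to be held at potential Hy's Law or stopped for good once Hy's Law is agreed

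*Combined protocol and SAP*

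**What the plan says.** The Introduction to Appendix B limits the appendix to identifying and reporting Hy's Law cases, and for management it states: "Specific guidance on the managing liver abnormalities can be found in Section 5.4.13 of the protocol".

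Appendix B defines potential Hy's Law as AST or ALT at or above 3 times the upper limit of normal together with total bilirubin at or above 2 times. When this is met, the investigator notifies the sponsor's representative, and "The Study Physician contacts the Investigator, to provide guidance, discuss and agree an approach" to follow-up. Monitoring, work-up, case report forms and, where serious, an SAE report follow. A joint review of alternative explanations has its own limit: "No later than 3 weeks after the biochemistry abnormality was initially detected, the Study Physician contacts the Investigator". If the information is delayed beyond that, "it is assumed that there is no alternative explanation until such time as an informed decision can be made", and an SAE is reported. When the review finds no other cause, the case is reported as an SAE: "As there is no alternative explanation for the HL case, a causality assessment of 'related' should be assigned".

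On dosing, Section 3.2 sets the default: olaparib is taken "without breaks (except as outlined for toxicity), for 90 days". Section 5.4.12, on non-hematological toxicity, says: "Treatment must be interrupted if any NCI-CTCAE grade 3 or 4 adverse event occurs which the investigator considers to be related" to study treatment. If toxicity returns after re-challenge and further interruption is judged inadequate, "then the patient should be considered for dose reduction or must permanently discontinue study treatment".

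**The concern.** Appendix B has a formal case definition, a notification chain and a joint causality review, yet none of its steps says what happens to the drug. The reader is sent elsewhere for that, and the section named is not there. Other organ systems do have a stated dosing action: interruption is recommended for unexplained pulmonary symptoms (5.4.12.1), dose reduction or discontinuation for renal impairment (5.4.8), and discontinuation for confirmed MDS/AML (5.4.11.3).

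At stake is the safety of men with potentially curable disease who are awaiting surgery. Following the plan to the letter, a man could keep taking olaparib while the cause of a potential Hy's Law case is reviewed. He could also be restarted after the review has agreed that nothing but olaparib explains the injury.

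**Working it through.** **Is the section really missing?** The headings run 5.4.12, 5.4.12.1 (pulmonary symptoms), 5.4.12.2 (nausea and vomiting), 5.4.12.3 (intercurrent events), then 5.5. The numbering is continuous, so the absence is not a product of removed pages. The reference may be a slip for 5.4.12. The protocol has other stale references: 6.7.1.3 in 5.4.11.1 and 5.4.11.2, 6.4.11 in 6.3.6, and 6.4.3 in 5.4.6. Even so, 5.4.12 and its subsections do not mention the liver.

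**Does any other text supply the action?**

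- *6.3.4 (events based on tests)*: says isolated elevations may need SAE reporting and refers to Appendix B. No dosing action.
- *6.3.6 (laboratory safety)*: asks for clinically significant abnormal values to be repeated, refers to Appendix B, and sends values needing dose modification to 6.4.11. That section does not exist; the likely target, 5.4.11, is hematological.
- *5.4.10*: toxicity could be managed by interruption or reduction. Permissive.
- *3.2, 5.4.6 and 5.7*: treatment may end at the investigator's discretion, or for an adverse event by decision of the Principal Investigator or sponsor. Permissive.
- *5.4.12*: mandatory interruption for a grade 3 or 4 event considered related. This can reach a liver case.
- *Appendix B*: agreed follow-up and SAE reporting. No dosing action.

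The count is: texts requiring a hold because potential Hy's Law is met, 0; texts requiring a permanent stop because Hy's Law is agreed, 0; general mandatory holds that may cover some liver cases, 1.

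**How far does the general hold reach?** It is triggered by CTCAE grade plus the investigator's own opinion on causality. Potential Hy's Law is defined in multiples of the upper limit of normal. The protocol adopts CTCAE v4.03 but does not reproduce its liver cut-offs, so the share of cases the hold would miss cannot be derived from the documents. Where it does apply, it requires interruption only and leaves re-challenge open.

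**Worst-case exposure**, if neither the investigator nor the Study Physician holds the drug before the 3-week review point:

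- Doses: 21 days × 2 per day = 42.
- Amount: 42 × 300 mg = 12,600 mg = 12.6 g.
- Planned course: 90 × 2 = 180 doses; 42 / 180 = 23%.

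**Effect of a mandatory hold on the treatment course** (no other interruption, surgery date unchanged):

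- Full 3-week hold: 90 − 21 = 69 days on drug. The replacement mark in 5.8 is 6 × 7 = 42 days, so 69 clears it.
- Permanent stop at the Day 30 visit: at most 30 + 5 = 35 days, below 42, so he is replaced under 5.8.
- Permanent stop at the Day 60 visit: 60 − 5 = 55 to 60 + 5 = 65 days, above 42, so 5.8 does not apply.
- Section 11.1.1 is stricter than 5.8. It admits to the efficacy set only men who took olaparib for the whole planned neoadjuvant period, and others may be replaced. The men with 69 days, or with 55 to 65, may fall outside it.

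**The case against.** The strongest reply is that the plan already protects these men. The hold in 5.4.12 turns on the investigator's own causality opinion, which is recorded for every adverse event, so it does not wait for the Appendix B review. An investigator who suspects olaparib in a grade 3 or 4 case must interrupt at once. Laboratory reports are reviewed without delay, the sponsor is notified, and the guidance step with the Study Physician is separate from the 3-week review. Authority to stop exists in several places, and after one continuous month off drug 5.7.1 leads to surgery. Liver injury is not an adverse event of special interest, as MDS/AML is, so the contrast with the MDS/AML stop carries limited weight.

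Most of this stands, and it rules out three stronger readings:

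- A reader might infer that liver events have no hold rule at all. The general rule in 5.4.12 covers some of them.
- A reader might infer that any hold must wait up to 3 weeks for causality. That limit governs the joint review, not the investigator's duty under 5.4.12.
- A reader might take 42 doses as the expected exposure. It requires both the investigator and the Study Physician to leave dosing unchanged for 3 weeks.

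The reply does not close the gap. Outside the grade 3 or 4 related case, every route to a hold is optional, and no route makes the stop permanent once Hy's Law is agreed.

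**Conclusion.** The point holds as a patient-safety gap that should be closed. The pointer is broken, and nothing requires a hold because potential Hy's Law is met or a permanent stop when Hy's Law is agreed. The second half is the firmer: even where the general hold applies, it ends in interruption, and restart after agreed drug-caused injury remains possible on the text.

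The size cannot be put as a number of men. Table 1 lists no hepatic reaction and the documents give no rate. The event is expected to be rare, and no case count is offered. The only figure is the conditional worst case of 42 doses (23% of the course).

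A reader might go on to infer harm to the primary result. The documents do not support that: the gap concerns dosing safety and does not bias the pCR estimate.

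**What to change.** Replace the reference to 5.4.13 with a short liver rule:

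- (a) When potential Hy's Law criteria are met, interrupt olaparib whatever the CTCAE grade or causality opinion. Do not restart unless the Appendix B review agrees an alternative explanation.
- (b) When Hy's Law is confirmed, discontinue permanently without re-challenge, and proceed to prostatectomy when clinically safe. Add this to the list in 5.7.

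If the review is still open after one continuous month off drug, 5.7.1 already applies.

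The cost is a text amendment, with no new visits or tests. A 3-week hold fits within the 4-week interruptions that 5.4.12 already allows. The downside is that a man whose elevation proves to have another cause loses doses during the review, up to 42 if it takes the full 3 weeks. He, or a man stopped permanently, may fall outside the 11.1.1 efficacy set and be replaced. Against a target of 15 that is one extra enrolment per case, and the same already applies to any toxicity hold.

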#### **Definitions**

#### Potential Hy's Law (PHL)

Aspartate Aminotransferase (AST) or Alanine Aminotransferase (ALT)  $\geq 3x$  Upper Limit of Normal (ULN) **together with** Total Bilirubin (TBL)  $\geq 2x$ ULN at any point during the study following the start of study medication irrespective of an increase in Alkaline Phosphatase (ALP).

#### Hy's Law (HL)

AST or ALT  $\geq$  3x ULN **together with** TBL  $\geq$  2xULN, where no other reason, other than the IMP, can be found to explain the combination of increases, eg, elevated ALP indicating cholestasis, viral hepatitis, another drug.

For PHL and HL the elevation in transaminases must precede or be coincident with (i.e. on the same day) the elevation in TBL, but there is no specified timeframe within which the elevations in transaminases and TBL must occur.

#### **Identification of Potential Hy's Law Cases**

In order to identify cases of PHL it is important to perform a comprehensive review of laboratory data for any patient who meets any of the following identification criteria in isolation or in combination:

• ALT  $\geq 3xULN$ 

- AST  $\geq 3xULN$
- TBL  $\geq 2xULN$

The Investigator will without delay review each new laboratory report and if the identification criteria are met will:

- Notify the AstraZeneca representative
- Determine whether the patient meets PHL criteria (see Definitions within this Appendix for definition) by reviewing laboratory reports from all previous visits
- Promptly enter the laboratory data into the laboratory CRF

